#### 6.2.15. Percentage of participants taking rescue medication within 24 hours postdose

##### 6.2.15.1. Main Analysis

- Estimand strategy: Not applicable (Section 2.2.2).
- Analysis set: EAS (Section 4). Participants in the EAS with first rescue medication date  $\leq$  study intervention start date + 1 day and missing first rescue medication time are excluded.
- Analysis methodology: The Mantel-Haenszel risk estimation stratified by country/region will be used. See details in Section 5.2.2. In addition, rescue medications will be tabulated by therapeutic class and preferred name.
- Intercurrent events and missing data: No relevant intercurrent is considered since taking rescue medication is the analysis objective.

Treatment group comparisons of the percentage of participants using rescue medication within 24 hours postdose will present similar statistics as the main analysis of the co-primary endpoint of pain freedom (see Section 6.1.1.1).

Rescue medications are concomitant medications that meet all the following criteria:

- “Rescue Medications” response to the question “Category” from the Concomitant Medications-Rescue Medicine CRF
- Taking rescue medication within 24 hours post dose is defined as rescue medication use  $\leq$  24 hours. No analysis window around the 24-hour postdose timepoint is used.

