### 2.2.2. Secondary Estimand(s)

The secondary efficacy estimands of this study are using composite estimands. The estimands are defined according to the secondary efficacy objectives and are in alignment with the following secondary endpoints. It includes the following 4+1 attributes:

- Treatment: Zavegepant and placebo;
- Population: All randomized participants with migraine headache of moderate or severe intensity who took study intervention;
  - For the objective of evaluating return to normal function, phonophobia freedom, photophobia freedom, and nausea freedom at 2 hours postdose, the population will be participants defined above who had functional disability (mildly impaired, severely impaired, or requires bedrest), phonophobia presence, photophobia presence, and nausea presence, respectively, at the time of dosing.
  - For the objective of evaluating pain relapse, the population will be participants defined above who had pain freedom at 2 hours postdose.
- Variable:
  - Percentage of participants with a pain intensity of none or mild (pain relief) at 15 minutes, 30 minutes, 60 minutes, 2 hours postdose, at all time points from 2 to 24 hours postdose, at all time points from 2 to 48 hours postdose, respectively.
  - Percentage of participants with a functional disability level of normal at 15 minutes, 30 minutes, 60 minutes and 2 hours postdose, respectively.
  - Percentage of participants with phonophobia absence, with photophobia absence, with nausea absence at 2 hours postdose, respectively.
  - Percentage of participants with a pain intensity of none (pain freedom) at all time points from 2 to 24 hours postdose, at all time points from 2 to 48 hours postdose, respectively.
  - Percentage of participants with a pain intensity of mild, moderate, or severe (pain relapse) at any time point after 2 hours postdose.

- Intercurrent event(s): Taking rescue medication at or before the corresponding assessed time points as specified in the endpoints postdose will be regarded as a failure.
- Population-level summary: Difference in percentage of participants achieving the specific outcome at time points of interest between zavegepant and placebo groups.

The secondary efficacy estimand for objective of rescue medication use is defined by the following attributes:

- Treatment: Zavegepant and placebo;
- Population: All randomized participants with migraine headache of moderate or severe intensity who took study intervention;

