### 5.2.3. Time-to-Event Analysis

Time-to-event distribution of endpoints (rescue medication use, pain freedom, MBS freedom, pain relief, normal function, phonophobia absence, photophobia absence, nausea absence) will be tabulated and plotted. Participants are considered to have an event through X hours ( $X=24$  hours or 8 hours) if the first post dose eDiary date/time defining a response is (1) at or before the upper bound of the X-hour analysis window in minutes (see Section 5.2.5), and (2) is before the imputed rescue medication start date/time, if not missing. Otherwise, participants who do not have an event through X hours are censored at the earliest of the following: (1) upper bound of the X-hour analysis window + 1 minute; (2) the imputed first rescue medication start date/time; (3) the last non-missing contact date/time.

For time to rescue medication use through 24 hours, participants are considered to have an event if the date/time of taking the rescue medication is prior to or at 24 hours post dose; otherwise, the time to rescue medication will be considered as censored at the earliest of the following: (1) 24 hours post dose + 1 minute, (2) the last non-missing contact date/time. For time to rescue medication use through 24 hours, the summary table and Kaplan-Meier plot will be using 2-hour time intervals: 0 to <2,  $\geq 2$  to <4,  $\geq 4$  to <6, ...,  $\geq 24$ . For exploratory endpoints through 8 hours, the summary table and Kaplan-Meier plot will be using the following time intervals: 0 to <15,  $\geq 15$  to <30,  $\geq 30$  to <45,  $\geq 45$  to <60,  $\geq 60$  to <90,  $\geq 90$  to <120,  $\geq 120$  to <180,  $\geq 180$  to <240,  $\geq 240$  to <360,  $\geq 360$  to <495, and  $\geq 495$  minutes.

The summary table will include the following statistics: number of participants at risk, number of participants with events, number of participants censored for each time interval; overall number and percentage of participants with events and censored; time-to-event estimate for median, first quartile, and third quartile with corresponding 95% CIs. The 95% CI will be estimated using the method of Brookmeyer and Crowley. The log-rank p-value will also be presented for comparison of zavegepant versus placebo. In the Kaplan-Meier plot, the percentage of participants for the endpoints within the time period postdose on the y-axis versus time in minutes on the x-axis will be displayed.

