### Rescue medication use within 24 hours post dose

- Rescue medication use within 24 hours post dose is defined as: first rescue medication date/time – intervention date/time (in hours)  $\leq$  24 hours. Participants with first rescue medication date  $\leq$  intervention date +1 day and missing first rescue medication time are excluded.

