### Appendix 2.1.2. Rescue Medication = Failure (RM=F) Algorithm

Efficacy assessments that are affected by the RM=F algorithm are pain intensity, nausea status, photophobia status, phonophobia status, and functional disability level.

Let X denote a postdose time point: 15, 30, 45, 60, or 90 minutes; 2, 3, 4, 6, 8, 24, or 48 hours.

If study intervention start date/time is from the eDiary Migraine Report, then it can be linked with its corresponding data at postdose time point X.

For a given assessment at time point X, the objective is to determine whether any rescue medication is taken at or before that assessment, even if the assessment is missing.

Rescue medication taken at or before time point X (RM=F) is defined as either (1) or (2):

- 1) Rescue medication taken at or before the assessment in the X analysis window. Defined as either of the following if the assessment is non-missing in the X analysis window:
  - (first rescue medication date/time  $\leq$  {eDiary finding date/time for the assessment in the X analysis window}, if first rescue medication time is not missing

- (first rescue medication date  $\leq$  {eDiary finding date for the assessment in the X analysis window}, if first rescue medication date is not missing but time is missing
- 2) Rescue medication taken at or before the missing assessment in the X analysis window. Defined as either of the following if the assessment is missing in the X analysis window:
  - (first rescue medication date/time – study intervention start date/time)  $\leq$  upper bound of the X analysis window (see [Table 2](#)), if first rescue medication time is not missing
  - first rescue medication date  $\leq$  study intervention start date + Y days, if first rescue medication date is not missing but time is missing
    - If X < 24 hours, then Y = 0.
    - If X = 24 hours, then Y = 1.
    - If X = 48 hours, then Y = 2.

090177e1a3a7d3d9\Approved\Approved On: 30-May-2025 05:10 (GMT)

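### The 24-hour rescue-use endpoint excludes participants recorded as taking rescue when only the clock time is missing, contrary to its estimand and to the RM=F date rule; rates are probably understated and the difference may be biased either way.

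*SAP*

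**What the plan says.** SAP 6.2.15.1 defines the analysis set as the EAS, then removes participants whose first rescue date is no later than "study intervention start date + 1 day and missing first rescue medication time are excluded". Appendix 2.1.1 repeats the rule in the derivation of the endpoint: a date up to "intervention date +1 day and missing first rescue medication time are excluded". The cut-off is a strict 24 hours: "No analysis window around the 24-hour postdose timepoint is used".

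Four other places bear on the same records.

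- **Estimand.** SAP 2.2.2 gives the population for the rescue-use estimand as "All randomized participants with migraine headache of moderate or severe intensity who took study intervention". Nothing is removed for a missing rescue time. Protocol 9.3.3 assigns the EAS to the secondary endpoints, SAP Appendix 1 lists plain EAS with observed data for this one, and SAP 2.1 declares no departure from the protocol analysis.
- **RM=F algorithm.** Appendix 2.1.2 has explicit handling for a first rescue date without a time ("if first rescue medication date is not missing but time is missing"). If the efficacy assessment is present, the rescue date is compared with the assessment date. If it is missing, the record counts as rescue when the date is no later than "study intervention start date + Y days, if first rescue medication date is not missing but time is missing", and "If X = 24 hours, then Y = 1".
- **Definition of rescue.** SAP 6.2.15.1 makes rescue medications a subset of concomitant medications, and SAP 6.5.1.5 defines those as taken on or after the start of study intervention.
- **Time to rescue.** The paragraph in SAP 5.2.3 on this analysis gives no rule for a missing time.

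**The concern.** A participant who took no rescue medication can never be excluded by this rule; only someone with a recorded rescue dose can. Selection into the analysis therefore depends on the outcome being estimated.

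For some of those removed nothing is in doubt. A postdose medication dated on the dosing day was taken within 24 hours, so the clock time is not needed to classify it. The rule still takes that certain event out of both numerator and denominator.

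The plan also treats one record in two ways. A participant with date-only rescue on the day after dosing will normally be a rescue failure for sustained pain relief from 2 to 24 hours, a key secondary endpoint, yet be absent from the endpoint that measures rescue use. What is at stake is whether the reported rescue rates, and the difference between arms, describe the population that the estimand names. No sensitivity analysis is planned to show how much the exclusion matters.

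**Working it through.** **Inputs.** The documents give no figure for this endpoint to reproduce: no expected rescue rate and no expected share of missing times. Both are assumed below. The 630 evaluable participants per group come from Protocol 9.5. The effect measure is a risk difference, zavegepant minus placebo (SAP 5.2.2). Stratification is ignored here.

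**Formula when every excluded participant is a true 24-hour user.** Let *r* be the true rescue rate in an arm of *N* and *m* the share of takers with no time. The rule drops *Nrm* participants, all of them takers, so

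reported rate = (Nr − Nrm) / (N − Nrm) = r(1 − m) / (1 − rm).

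For r = 0.22 and m = 0.10: 0.198 / 0.978 = 20.2%. For r = 0.30 and m = 0.10: 0.270 / 0.970 = 27.8%. The numbers dropped are 630 × 0.22 × 0.10 ≈ 14 and 630 × 0.30 × 0.10 ≈ 19.

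| True rates (zavegepant / placebo) | Time missing among takers | Reported rates | Reported difference | True difference |
|---|---|---|---|---|
| 22% / 30% | 2% / 2% | 21.7% / 29.6% | -7.9 | -8.0 |
| 22% / 30% | 10% / 10% | 20.2% / 27.8% | -7.6 | -8.0 |
| 60% / 70% | 10% / 10% | 57.4% / 67.7% | -10.3 | -10.0 |
| 30% / 40% | 10% / 5% | 27.8% / 38.8% | -10.9 | -10.0 |
| 30% / 40% | 5% / 10% | 28.9% / 37.5% | -8.6 | -10.0 |
| 40% / 40% | 10% / 5% | 37.5% / 38.8% | -1.3 | 0.0 |

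**Direction of the difference.** With equal *m*, the slope of the reported rate in *r* is (1 − m)/(1 − rm)². It equals 1 at r = (1 − √(1 − m))/m, which is 0.50 to 0.53 for *m* between 2% and 20%. Below about 50% the difference shrinks; above it, the difference grows. Unequal missingness can move it either way, and can create a difference where none exists.

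**When some excluded participants are not 24-hour users.** Let *e* be the share of the arm excluded and *q* the fraction of those who truly used rescue within 24 hours. Then

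reported rate = (r − eq) / (1 − e).

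With r = 40% and e = 4%: q = 1 gives 37.5%, q = 0.5 gives 39.6% and q = 0.2 gives 40.8%. The rate is understated whenever *q* exceeds *r*. Dosing-day records have q = 1. Next-day records do not: after an 08:00 dose, only the first 8 hours of the next calendar day lie within 24 hours.

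**The case against.** **Readings the documents do not support.** A reader might infer that the rule pulls the treatment difference toward zero. That needs equal missingness in the two arms and rescue rates below about 50%, and the documents state neither. A reader might also infer that every excluded record lowers the rate. That is certain for dosing-day records only; a next-day record may fall after 24 hours, and dropping such a participant raises the rate.

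**The RM=F comparison has limits.** The offset Y = 1 applies only when the 24-hour assessment is missing. Otherwise the rescue date is compared with the assessment date, which for a 23-to-25-hour window is normally the next day, so the two branches usually agree. Appendix 2.1.2 also does not list rescue use among the assessments it governs, and counting an uncertain record as a failure is natural under a composite strategy. Different handling where rescue is itself the outcome is not automatically a contradiction. That is fair, but it justifies care over next-day records, not removal of dosing-day events.

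**The time-to-event text should not be over-read.** The phrase "the imputed first rescue medication start date/time" in SAP 5.2.3 belongs to the general censoring paragraph. The time-to-rescue paragraph does not mention imputation, so the gap there is a missing rule, not a conflicting one.

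**Little may depend on it.** Protocol 6.9.2 requires the date and time of rescue to be recorded, and the paper diary is reviewed at the EOT Visit, so few times may be missing. At 22% and 30% with 10% missing, the shift is 0.4 points against a standard error of √(0.22 × 0.78/630 + 0.30 × 0.70/630) ≈ 2.5 points. The endpoint is other secondary, unadjusted and outside the testing hierarchy, and the exclusion is prespecified and stated consistently in two places. All of this stands. It limits the consequence; it does not make the rule correct.

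**Conclusion.** The exclusion is wrong as written. It selects on the outcome, discards dosing-day users who can be classified with certainty, and leaves a set that is not the estimand population. The rescue rate is probably understated in both arms; this is not certain, because it depends on how many next-day records fall within 24 hours. The bias in the difference has no determined direction: it depends on the rescue rates and on whether missing times are equally common in the two arms.

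In the equal-missingness examples above the shift in the difference is at most 0.4 points; with 10% against 5% missing it is about 0.9 to 1.4 points. All of these sizes rest on assumed rates and assumed missingness, and on treating every excluded participant as a 24-hour user. Because the endpoint is descriptive, no confirmatory conclusion changes.

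**What to change.** In SAP 6.2.15.1 and Appendix 2.1.1, delete the exclusion and state instead:

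- All EAS participants are retained.
- Postdose rescue dated on the dosing day with a missing time counts as use within 24 hours.
- Rescue dated the next day with a missing time counts as use in the main analysis, in line with the RM=F date rule.
- One sensitivity run counts those next-day records as non-use. With the main analysis, this brackets the part of each arm's rate that is uncertain because of missing times.

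In SAP 5.2.3, add a matching rule for time to rescue that also assigns an event time to date-only records. Classifying a record as use is not enough for a Kaplan-Meier analysis, so the convention has to be stated.

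Reporting the number of date-only records by arm and by day would let a reader judge the effect directly. The cost is a few sentences in the SAP, one changed derivation and one extra run. No new data are needed, and Appendix 1, which already lists the EAS, can stay as it is.

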#### 6.2.15.2. Supportive Analysis

Time to rescue medication use through 24 hours postdose is assessed by treatment group using the approach as described in Section 5.2.3. Rescue medication use through 24-hours postdose is considered as an event.

#### 6.2.16. Percentage of participants with a pain intensity of none or mild at 60 minutes postdose

- Estimand strategy: Composite policy (Section 2.2.2).
- Analysis set: EAS (Section 4).
- Analysis methodology: The Mantel-Haenszel risk estimation stratified by country/region will be used. See details in Section 5.2.2.
- Intercurrent events and missing data: (1) Taking rescue medication at or before 60 minutes postdose (RM=F; see Appendix 2.1) and (2) missing pain intensity at 60 minutes postdose (NC=F; see Section 5.3 for definition) will be regarded as failures.

Treatment group comparisons of the percentage of participants with pain relief at 60 minutes postdose (i.e., in the 60-minute analysis window) will present similar statistics as the main analysis of the co-primary endpoint of pain freedom (see Section 6.1.1.1).

#### 6.2.17. Return to normal function at 15 minutes postdose

- Estimand strategy: Composite policy (Section 2.2.2).
- Analysis set: EAS (Section 4). Participants with functional disability at the time of dosing will be included.
- Analysis methodology: The Mantel-Haenszel risk estimation stratified by country/region will be used. See details in Section 5.2.2.

- Intercurrent events and missing data: (1) Taking rescue medication at or before 15 minutes postdose (RM=F; see [Appendix 2.1](#)) and (2) missing functional disability level at 15 minutes postdose (NC=F; see [Section 5.3](#) for definition) will be regarded as failures.

Treatment group comparisons of the percentage of participants with return to normal function at 15 minutes postdose (i.e., in the 15-minute postdose analysis window) will present similar statistics as the main analysis of the co-primary endpoint of pain freedom (see [Section 6.1.1.1](#)).

### 6.3. Exploratory Endpoints

#### 6.3.1. Percentage of participants with a pain intensity of none at 15 minutes, 30 minutes, 45 minutes, 60 minutes, 90 minutes, 2 hours, 3 hours, 4 hours, 6 hours, 8 hours, 24 hours, and 48 hours postdose

##### 6.3.1.1. Main Analysis

- Estimand strategy: Composite policy ([Section 2.2.3](#))
- Analysis set: EAS ([Section 4](#)).
- Analysis methodology: The Mantel-Haenszel risk estimation stratified by country/region will be used. See details in [Section 5.2.2](#).
- Intercurrent events and missing data: (1) Taking rescue medication at or before each of the assessed time points postdose (RM=F; see [Appendix 2.1](#)) and (2) missing pain intensity at each of the assessed time points postdose respectively (NC=F; see [Section 5.3](#) for definition) will be regarded as failures.

Treatment group comparisons of the percentage of participants with pain freedom at each time point from 15 minutes through 48 hours postdose (i.e., in the 15-minute to 48 hours postdose analysis window) will present similar statistics as the main analysis of the co-primary endpoint of pain freedom (see [Section 6.1.1.1](#)).

##### 6.3.1.2. Supportive Analysis

Time to pain freedom through 8 hours postdose distribution will be presented, separately. Kaplan-Meier plot will also be displayed (see [Section 5.2.3](#) for details).

#### 6.3.2. Percentage of participants with an MBS reported before dosing that is absent at 15 minutes, 30 minutes, 45 minutes, 60 minutes, 90 minutes, 2 hours, 3 hours, 4 hours, 6 hours, 8 hours, 24 hours, and 48 hours postdose

##### 6.3.2.1. Main Analysis

- Estimand strategy: Composite policy ([Section 2.2.3](#)).

- Analysis set: EAS (Section 4).
- Analysis methodology: The Mantel-Haenszel risk estimation stratified by country/region will be used. See details in Section 5.2.2.
- Intercurrent events and missing data: (1) Taking rescue medication at or before each of the time points postdose (RM=F; see Appendix 2.1) and (2) missing MBS status at each of the time points postdose respectively (NC=F; see Section 5.3 for definition) will be regarded as failures.

Treatment group comparisons of the percentage of participants with MBS at each time point from 15 minutes through 48 hours postdose (i.e., in the 15-minute to 48 hours postdose analysis window) will present similar statistics as the main analysis of the co-primary endpoint of pain freedom (see Section 6.1.1.1).

#### 6.3.2.2. Supportive Analysis

Time to MBS freedom through 8 hours postdose distribution will be presented. Kaplan-Meier plot will also be displayed (see Section 5.2.3 for details).

#### 6.3.3. Percentage of participants with a pain intensity of none or mild (pain relief) at 15 minutes, 30 minutes, 45 minutes, 60 minutes, 90 minutes, 2 hours, 3 hours, 4 hours, 6 hours, 8 hours, 24 hours, and 48 hours postdose

##### 6.3.3.1. Main Analysis

- Estimand strategy: Composite policy (Section 2.2.3).
- Analysis set: EAS (Section 4).
- Analysis methodology: The Mantel-Haenszel risk estimation stratified by country/region will be used. See details in Section 5.2.2.
- Intercurrent events and missing data: (1) Taking rescue medication at or before each of the time points postdose (RM=F; see Appendix 2.1) and (2) missing pain intensity at each of the time points postdose respectively (NC=F; see Section 5.3 for definition) will be regarded as failures.

Treatment group comparisons of the percentage of participants with pain relief at each time point from 15 minutes through 48 hours postdose (i.e., in the 15-minute to 48 hours postdose analysis window) will present similar statistics as the main analysis of the co-primary endpoint of pain freedom (see Section 6.1.1.1).

##### 6.3.3.2. Supportive Analysis

Time to pain relief through 8 hours postdose distribution will be presented, separately. Kaplan-Meier plot will also be displayed (see Section 5.2.3 for details).

### **6.3.4. Percentage of participants with a functional disability level of normal at 15 minutes, 30 minutes, 45 minutes, 60 minutes, 90 minutes, 2 hours, 3 hours, 4 hours, 6 hours, 8 hours, 24 hours, and 48 hours postdose**

#### **6.3.4.1. Main Analysis**

- Estimand strategy: Composite policy (Section 2.2.3).
- Analysis set: EAS (Section 4). Participants with functional disability at the time of dosing will be included.
- Analysis methodology: The Mantel-Haenszel risk estimation stratified by country/region will be used. See details in Section 5.2.2.
- Intercurrent events and missing data: (1) Taking rescue medication at or before each of the time points postdose (RM=F; see Appendix 2.1) and (2) missing functional disability level at each of the time points postdose respectively (NC=F; see Section 5.3 for definition) will be regarded as failures.

Treatment group comparisons of the percentage of participants with return to normal function at each time point from 15 minutes through 48 hours postdose (i.e., in the 15-minute to 48 hours postdose analysis window) will present similar statistics as the main analysis of the co-primary endpoint of pain freedom (see Section 6.1.1.1).

